#### 14.4 Adverse Event Assessment

Any AE experienced after the first UroLift device is introduced (enrolment) will require reporting on the eCRF. In general, a primary diagnosis for the event should be reported instead of each symptom, with the exception of LUTS. Lower urinary tract symptoms should be reported individually per the elements of IPSS. Only exacerbated conditions or new onset qualify as an AE, but if patient history is in question, report AE conservatively.

Adverse events will be summarised by overall adverse events (AEs), severe AEs (grade 3 or higher on CTCAE scale (See **Table 11**), AEs related to device and/or procedure (See **Table 9**), serious adverse events (SAEs) and SAEs related to device and/or procedure. Adverse events will be coded using MedDRA and Common Terminology Criteria for Adverse Events (CTCAE) severity grades and will be presented by System Organ Class (SOC) and preferred term.

Principal Investigators will be responsible for assessing severity via the CTCAE scale (**Table 11**) and Relatedness (**Table 9**).

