**Table 6 Pre-Procedure Activities\***

*Includes data collection and procedures that don't determine eligibility		
Activity	Considerations and instructions	Time Frame
Sexual Function Questionnaire	
 
• A baseline SHIM should be completed if patients are sexually active within the previous 6 months.
 
	
 
• Recall period of 6 months; complete in screening as applicable.
 

Urodynamics	
 
• Determine the grade of bladder outlet obstruction (BOO) and to assess detrusor contractility function
 
	
 
• During screening, after consent, within 30 days of index procedure.
 
• Urodynamics testing may be performed at each study site if a testing facility is available and a qualified operator is on-site.
 

Medications	
 
• BPH, LUTS; Sexual Function; GU; should be captured.
 
	
 
• Collect through 10 years history of non-transient prescriptions with approximate duration and indication.
 

Alpha Blocker	
 
• It is required that subject was on alpha blocker at a minimum, through previous failed TWOC.
 
	
 
• Alpha blockers should be prescribed per site's standard of care throughout the duration of the study. Initiation and cessation should be documented on the concomitant medication log.
 

Aspirin	
 
• If patient on regular dose <math>\leq</math> 100 mg no washout required.
 
• If patient takes PRN, instruct patient to avoid.
 
	
 
• 3 days prior to index procedure
 

Anticoagulants	
 
• Patient should be cleared to washout or, excluded.
 
	
 
• 3 days prior to procedure
 

Catheter use	
 
• Record history, type, duration, indication, of catheter, reason out
 
	
 
• Most recent
 

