### 10.3 Enrolment

A subject is considered enroled if he has signed the approved informed consent form to participate in the study, has met all inclusion and exclusion criteria, and the first UroLift delivery device has been inserted. Once subject is enroled, adverse events need to be documented and reported.

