## 10.8 12 Month Follow-up Procedures

The following evaluations will be performed at **12 months (± 30 days)** post index procedure:

- If subject is scheduled for or has already undergone alternative surgical procedure, see also section **10.10.1**.
- Questionnaires to be completed by the subject:
  - Urinary Symptoms questionnaires including IPSS & QoL (International Prostate Symptoms Score with Quality of Life) and BPHII (Benign Prostatic Hyperplasia Impact Index) unless current indwelling catheter.
  - SHIM (Sexual Health Inventory for Men): Recall over the last 6 months. Completed if subject was sexually active at baseline.
  - Patient Satisfaction
  - Symptom questionnaires upon occurrence (includes: Incontinence Severity Index (ISI), haematuria, dysuria, pelvic pain VAS).
- Relevant Concomitant medications: BPH/LUTS; Sexual Function; GU; Prostate Cancer
- Freestanding uroflow and post void residual (PVR) unless current indwelling catheter or adverse event does not permit.
- Urinalysis (urine culture and sensitivity if abnormal, clinically significant and indicates a urinary infection). UA not required if current indwelling catheter.
- Digital Rectal Exam (DRE)
- Urodynamics testing, if applicable to site

- Cystoscopy (flexible)
- Voiding Assessment
- Catheterisation Review
- Adverse Event Review; Intervention Review

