 Can perform day of procedure prior to (index) UroLift procedure to reduce site and subject burden.

 TWOC should be repeated per standard of care if first attempt unsuccessful.

 Urodynamics testing may be performed at each study site if a testing facility is available and a qualified operator is on-site.

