### 13.2 Anticipated Adverse Events

---

Adverse events will be solicited from the subject and documented after enrolment (see section 14 Adverse Events) the UroLift System Treatment, and at each follow-up time point. The risks of the undergoing the PUL procedure as part of this study are the same as having the procedure without being in the study.

Possible anticipated adverse events may be, but are not limited to those symptoms or events related to the disease process, the procedure (Section 13.3), device use (Section 13.5), reactions to medication inclusive of anaesthesia, and/or the study testing.

Anticipated adverse events that are: (1) reflective of the disease process (such as exacerbation of LUTS) and/or (2) inherent to this and any prostatic invasive procedure and expected to occur in this subject population are still to be reported as AEs during this study.

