### 13.4 Protocol Required Testing with Anticipated Adverse Events

---

Possible anticipated adverse events related to urodynamic testing are discomfort passing urine, urgency, frequency, bladder spasms, lower urinary tract symptoms, haematuria, and urinary tract infection.

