## 20 Termination of Study

---

The study will be terminated after the following milestones have been met; a) all active subjects have completed their 12 month study visit and b) completion of the final study report and c) study centres are closed. Investigators will be notified by Sponsor of study termination for any other reason.

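### Adverse events before the first device, and delayed events after the 12-month tests, have no clear reporting route

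*Combined protocol and SAP*

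**What the plan says.** The start of collection is stated the same way throughout. Enrolment under Section 10.3 requires signed consent, all criteria met, "and the first UroLift delivery device has been inserted", and the duty to report follows from enrolment. Section 14.4 repeats it: "Any AE experienced after the first UroLift device is introduced (enrolment) will require reporting on the eCRF". Section 14.5 collects AEs on enrolled subjects and sends SAE notification to the sponsor through the AE form. The safety population in Section 16.3 also requires that a device was introduced.

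The end is the end of follow-up (Table 2). Table 7 marks AE review from the index procedure to the 12-month visit and leaves the Screening and Study Exit cells empty. Under Section 20, the first condition for closing the study is that "all active subjects have completed their 12 month study visit".

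Section 13 names risks that arise near or beyond these limits. Section 13.2 includes "reactions to medication inclusive of anaesthesia, and/or the study testing" among the sources of anticipated events. Section 13.4 is specific: "Possible anticipated adverse events related to urodynamic testing are discomfort passing urine, urgency, frequency, bladder spasms", and its list continues to haematuria and urinary tract infection.

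Table 6 places baseline urodynamics as follows: "During screening, after consent, within 30 days of index procedure". Footnote 4 of Table 7 allows urodynamics, ultrasound and cystoscopy on the index day instead: "Can perform day of procedure prior to (index) UroLift procedure to reduce site and subject burden". Section 10.8 lists "Urodynamics testing, if applicable to site" and flexible cystoscopy at 12 months.

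**The concern.** The protocol asks men to accept tests with stated risks, then defines a reporting window that opens after the first round of tests and has its last review at the same visit as the second. Table 6 says its activities do not determine eligibility, so baseline urodynamics is done for the study's purposes. If a man were admitted with an infection after that test, the text as written would not require an SAE report. If he then failed screening, he would have no AE record at all.

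What is at stake is mainly participant protection. The sponsor's duty in Section 14.5 to pass on SAEs, and to suspend the study for an unreasonable risk, depends on events reaching it. A lesser stake is the completeness of the procedural safety record for PUL, which Section 16.6 sets against the surgical charts.

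**Working it through.** No sample-size, power or error-rate calculation applies. The check sets the reporting window against the timing of each exposure.

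**Window.** Table 7 marks AE review at 6 points: index procedure, 3 days, 6 weeks, 3 months, 6 months and 12 months. Points before the index procedure: 0. Points after the 12-month visit: 0.

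**Exposures.**

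| Exposure | Timing | Covered? |
|---|---|---|
| Baseline urodynamics before the index day (optional by site) | After consent, up to 30 days before index | No. It precedes enrolment and there is no Screening review |
| Baseline urodynamics or cystoscopy on the index day | Before the first device | Events starting after the first device are covered; earlier ones are not under 14.4 |
| Anaesthesia, pre-procedure cystoscopy, sheath insertion | Before the first device | Unclear if the man enrols; no if he receives no device |
| 12-month urodynamics (optional by site) and flexible cystoscopy | Last visit | Immediate events yes, through the review at that visit; delayed events no |

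**Event before the index day, man enrols.** Table 5 asks for each AE to be judged pre-existing or new, and Section 14.4 counts only new or worsened conditions. An infection that began in screening can therefore become medical history.

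**Event before the first device, man never enrols.** He falls outside Sections 10.3, 14.5 and 16.3. This can happen in practice, because Table 5 allows the cystoscopy that rules out an obstructing median lobe to be done on the index day.

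**Event before the first device, man enrols.** Section 10.3.4 asks for complications and adverse events in the procedural data and states no starting point. Table 7 has an AE review in the index-procedure column. Section 14.4 sets a later start. The text does not say which governs.

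**Link to the primary safety measure.** Section 6.3 uses SAEs related to the BPH intervention through 3 months. Urodynamics is not a BPH intervention, and the 12-month tests fall outside 3 months. Of the three gaps, only an anaesthetic or instrumentation SAE before the first device could enter this measure.

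**The case against.** The strongest reply is that the plan is explicit and coherent. Section 13.2 itself says events are documented after enrolment, so listing a risk there is no promise to collect it earlier, and Section 14.5 describes a CE-marked device in a post-market study. That is fair: a reader might infer that Section 13 contradicts Section 14, and it does not. The point is that a clearly stated rule leaves a safety gap.

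Much is also captured already. Once the first device is in, events are recorded whatever their cause (14.5), so a later infection or anaesthetic complication is collected. The 12-month visit has its own review. Medical history is updated up to the procedure (Table 5), screen-failure reasons are examined after 15 subjects (16.1), and source documents are monitored (17.3). These narrow the gap, but none gives a route for an SAE in a man who has not received a device.

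Four stronger readings are tempting and unsupported:

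- **Bias favouring PUL.** Surgical charts are abstracted for the procedure with no device-type starting point (15.8.2), so a reader might infer that PUL rates are lower by construction. But the charts yield only certain AE types, where available, while PUL men are asked at every visit. These differences can lower the surgical rates, so no net direction can be claimed.
- **A count of missed infections.** The documents give no infection rate and no number of men tested, and testing depends on a site having the facility and operator.
- **Misattribution to PUL.** Table 9 has no category for study testing, but its lower grades allow for other causes and an independent urologist adjudicates relatedness (14.6). No new category is needed.
- **Test safety as a study aim.** Sections 6.1 and 7 list feasibility, endpoint, design and conduct. They do not list the safety of urodynamics or cystoscopy.

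**Conclusion.** The concern holds in a limited form. As written, three kinds of event lack a reporting route: (i) events from urodynamics between consent and the index day, at sites that perform it; (ii) anaesthetic, cystoscopy or sheath events before the first device, certain when no device follows and ambiguous otherwise; (iii) delayed events after the 12-month tests.

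The number of men affected is unknown. The effect on the primary safety measure is probably small, resting on the judgement that a serious anaesthetic or instrumentation event before the first device is rare; the documents give no rate. The case for change is participant safety and a complete record, not a distorted primary result. The conclusion applies to the prospective cohort only and assumes that no separate safety document, such as the Safety Plan mentioned in Section 14.6, starts collection earlier.

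**What to change.** - In Sections 10.3, 14.4 and 14.5, collect from consent all SAEs and any AE related to study testing, anaesthesia or instrumentation, including in men who then fail screening.
- Add an AE-review mark in the Screening column of Table 7.
- Reconcile Sections 10.3.4 and 14.4 by stating that index-day events from the start of anaesthesia count as procedural events, both in the PUL record and in the comparison with surgery. Tabulate earlier pre-device events separately, so that the safety population in Section 16.3 can stay as it is.
- Allow events reported shortly after the 12-month urodynamics or cystoscopy to be recorded before Study Exit. A brief telephone check would help but is optional.

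The cost is protocol wording, one schedule entry and AE forms for consented men who are not enrolled. A few more events will be reported, and the PUL event rate may look slightly less favourable.

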**Table 9 Device and Procedure Relatedness Definitions**

- Highly probable -- The AE follows a reasonable temporal sequence from receipt (or attempted receipt) of the device treatment or procedure.
- Probable -- The AE follows a reasonable temporal sequence from receipt of the device treatment or procedure and the possibilities of factors other than the device treatment or procedure, such as underlying disease, concomitant drugs, or concurrent treatment can be excluded.

 National Cancer Institute, Common Terminology Criteria for Adverse Events v4.0 NCI, NIH, DHHS. May 29, 2009; NIH publication # 09-7473. The reprint of the terminology will be part of manual of operations (MOP).

- Possible -- The AE follows a reasonable temporal sequence from receipt of the device treatment or procedure and the possibility of device treatment or procedure involvement cannot be excluded. However, other factors such as underlying disease, concomitant medications, or concurrent treatment are presumable.
- Unlikely -- The AE has an improbable temporal sequence from receipt of the device treatment or procedure, or it can be reasonably explained by other factors, including underlying disease, concomitant medication, or concurrent treatment.
- Not related -- The AE has no temporal sequence from receipt of the device treatment or procedure, or it can be explained by other factors, including underlying disease, concomitant medication, or concurrent treatment

## 14.5 Adverse Event Reporting

Adverse events will be collected on all enroled subjects. Subjects will be asked about adverse events at each visit, and all AEs will be documented and reported regardless of relatedness.

Adverse events will be documented on the AE electronic case report form (eCRF) within the study's Electronic Data Capture System (EDC).

When an SAE occurs, the Sponsor should be notified within 24 hours of site awareness via completion of the AE eCRF in the EDC System. Sponsor will receive an alert upon any SAE entry and will be responsible for reporting to notified body, ethics committee and all other participating investigators as applicable. Should Sponsor determine, either through investigator reports or in-house testing, that a unexpected SAE presents an unreasonable risk to all participating subjects, Sponsor will suspend the clinical investigation.

It is the responsibility of the Chief Principal Investigator to report all related and unexpected Serious Adverse Events (SAEs) to the ethics committee. The Sponsor may report on behalf of the Chief Investigator. Device-related SAEs in this study, using a CE-marked device in a post-market surveillance study, are reportable to the MHRA Adverse Incident Centre as reported under the requirements of the Devices Vigilance requirement.

Annual and final reports will be provided to the EC as applicable per EC requirements with Sponsor assistance.

## 14.6 Adverse Event Independent Reviewer

---

An independent reviewer will be employed for safety review. The independent reviewer will provide comprehensive medical review and adjudicate the reported adverse events. The assessments of the independent reviewer will help to ensure that the adverse event data is accurate, free of bias, and consistently reported across the participating study centres. This independent reviewer will be an independent urologist, with no ties to Sponsor or any of the participating ECs or third party providers. A Safety Plan that describes the adjudication conventions will be established. The independent reviewer will review events, with the support of redacted source documents, to determine AE/SAE/UAE classification, event relatedness, degree of relatedness, event severity, and MedDRA coding. Adjudication will occur ongoing throughout the study and to be completed in advance of the study final report.

Adverse Events with onset within 90 days of Index Procedure will be evaluated by independent reviewer per the Clavien-Dindo (CD) classification (**Table 10**).

The independent reviewer may also categorize by CTCAE classification (**Table 11**). Complications, outside the recovery course, will be assigned a CD grade.

**Table 10 Clavien Dindo Classification of Surgical Complications (Daniel Dindo, 2004)**

Complication Definition	Description
Sequelae Definition	Inherent events to the procedure (will not be assessed further). Example being mild haematuria that resolves without treatment.
Grade Level for Complications	
I	Any deviation from the normal postoperative course without the need for pharmacological treatment or surgical, endoscopic, and radiological interventions
II	Requiring pharmacological treatment with drugs other than such allowed for grade I complications (e.g. change in antibiotics), blood transfusions and total parenteral nutrition.
III	Requiring surgical, endoscopic or radiological intervention
IIIa	Intervention not under general anaesthesia
IIIb	Intervention under general anaesthesia
IV	Life –threatening complication (including CNS complications)* requiring IC/ICU management
IVa	Single organ dysfunction (including dialysis)
IVb	Multi-organ dysfunction
V	Death of a patient
Suffix "d"**	If the patient suffers from a complication at the time of discharge, the suffix d (for disability) is added to the respective grade of complication. This label indicates the need for a follow-up to fully evaluate the complication.

\*Brain hemorrhage, ischemic stroke, subarachnoidal bleeding, but excluding transient ischemic attacks. CNS, central nervous system; IC, intermediate care; ICU, intensive care unit.  
 \*\* For purposes of this study Suffix "d" will not be used.

**Table 11 Common Terminology Criteria for Adverse Events Definition**

Grade	Guidance
1	Mild; asymptomatic or mild symptoms; clinical or diagnostic observations only; intervention not indicated.
2	Moderate; minimal, local or non-invasive intervention indicated;

Grade	Guidance
	Limiting age-appropriate instrumental ADL*.
3	Severe or medically significant but not immediately life-threatening; hospitalisation or prolongation of hospitalisation indicated; disabling; limiting self-care ADL*.
4	Life-threatening consequences; urgent intervention indicated.
5	Death related to AE
*Activities of Daily Living (ADL)	
Instrumental ADL	Refers to preparing meals, shopping for groceries or clothes, using the telephone, managing money, etc.
Self-care ADL	Refers to bathing, dressing and undressing, feeding self, using the toilet, taking medications, and not bedridden.

## 14.7 Device Malfunctions, Failures, or Near Incidents

All device failures or malfunctions will be documented on the appropriate case report form and reported to Sponsor within 24 hours of occurrence. The malfunctioning device involved in the incident will be returned to Sponsor for evaluation, as available. Any unexpected Serious Adverse Event (SAE) occurring as a result of device deficiencies will be reported to the Competent Authorities in accordance with the European Medical Devices directives (93/42/EEC) and all applicable national regulations.

Refer to the manual of operations (MOP) for device return to Sponsor instructions.

## 15 Study Procedures – Retrospective Cohort

The retrospective chart review will provide a dataset for comparison to specific outcomes in the UroLift cohort. The target population for this arm is BPH patients that presented with AR and went on to de novo invasive surgery from June 1, 2015 to December 31, 2015. Baseline health status through 12 months post-procedure will be collected for those patients meeting criteria.

### 15.1 Qualifications for Case Abstractors

Case abstractors will be qualified by education or experience to abstract protocol-required information from the medical records; these qualifications will be documented. Case abstractors will be delegated by the Principal Investigator and trained prior to conducting study-specific activities.

## 15.2 Subject Identification

Case abstractors will create a Master List of all invasive BPH surgeries (TURP, HoLEP, etc.) performed by the site from June 1, 2015 to December 31, 2015. Each case will be reviewed against the study selection criteria (See Section 15.3) and case abstractors will document enrolment status for each subject and the reason(s) for that decision. Patients meeting criteria will be contacted for consent.

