#### 4 Introduction

Benign prostatic hyperplasia (BPH) impacts quality of life by causing lower urinary tract symptoms (LUTS). The number of U.S. men with symptomatic BPH that seek treatment options is projected to

increase from 8.1 million in 2010 to 10.3 million in 2020. Current treatment options consist of watchful waiting, medical therapy and interventional procedures. Watchful waiting is generally reserved for those with mild symptoms. Over 4 million U.S. men are on medical therapy for BPH. While symptom relief is modest with an American Urological Association Symptom Index (IPSS) improvement at 1 year of 3.5-7.5 vs. 0-5.7 for placebo, the incidence of side effects along with inadequate relief prompt over one-quarter of men on drug therapy to discontinue treatment early.

Most surgical approaches remove prostate tissue and, while highly effective, present with significant morbidity. The gold standard remains transurethral resection of the prostate (TURP) that is associated with a 14.9 point improvement in IPSS at 1 year. This improvement, however, also comes with a 20% rate of perioperative morbidity and long-term complications that include urinary incontinence (3%), urethral stricture (7%), erectile dysfunction (10%) and ejaculatory dysfunction (65%). Because tissue is removed and underlying tissue injured, there is a healing response and tissue inflammation such that subjects experience routine catheterisation and irritative symptoms post-procedure. For these reasons, the number of TURP surgeries among the US Medicare population has been declining (from 72,163 in 1999 to 49,683 in 2005). Laser vaporisation is a newer approach to TURP that minimises blood loss compared to conventional TURP, but still typically requires general or spinal anaesthesia and overnight hospital stay. There is routine catheterisation and post-operative dysuria, again as a result of tissue removal and injury. US Medicare data show that from 2005 to 2007, conventional TURP surgeries decreased by over 12,600 procedures while laser vaporisation procedures increased by over 12,100 procedures. Thus, laser vaporisation has been employed more as a

---

 Roehrborn, C.G., Current medical therapies for men with lower urinary tract symptoms and benign prostatic hyperplasia: achievements and limitations, *Rev Urol* 2008; 10:14.

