### 10.3.3 Training in Prostatic Urethral Lift Procedure

Selected Principal Investigators in the study will have performed a minimum of 30 UroLift procedures. Each will have undergone the NeoTract Professional Education Program.

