## 13.8 Risk Mitigation

---

Clinical risks will be minimised by careful assessment of the subject prior to, during, and after the procedure. Careful follow-up will help minimise risks associated with changing conditions of the subject. Proper subject selection will be achieved by following the subject inclusion and exclusion criteria. Participating Investigators are highly experienced UroLift operators and experienced in clinical research. The study centres have adequate resources and facilities to safely conduct study with compliance.

The UroLift System itself has safety features. The delivery device can't be deployed without switching the safety trigger off and features a bypass suture cutting mechanism. Users are able to manually retract needle if necessary. All of these features are detailed in the instructions for use.

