## 15.3 Modified Enrolment Criteria for Retrospective Arm

### 15.3.1 Retrospective Inclusion Criteria

Patients enroled in this study must meet the following criteria:

1. Male gender
2. Diagnosis of symptomatic BPH
3. Age  $\geq$  50 years
4. Presented with acute urinary retention with at least one failed trial without catheter prior to invasive surgery (index procedure)
5. Underwent invasive BPH surgery (TURP, HoLEP, etc.) while in retention and performed by site between June 01, 2015 and December 31, 2015.
6. Prostate volume  $\leq$  100 cc as measured by ultrasound, specimen (tissue) weight, or other standard method for prostate evaluation

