### 15.8.2 Procedure

The following will be collected (if available):

• Date, duration	• Type of facility, type of surgery	• Complications, adverse events (urological, sexual function, cancer and SAEs)	• Duration of hospital stay
• Catheterisation	• Pathology (documentation only)		

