## 17.2 Investigator and Site Personnel Training

---

Investigators responsible for treating subjects with the UroLift System have expert experience with the device. A proctoring of the first case will be performed by a NeoTract representative to ensure proper data collection.

The training of appropriate clinical site personnel to the study will also be the responsibility of Sponsor. The Investigator is responsible for ensuring that his/her staff conduct the study according to the protocol and are qualified to perform their delegated study activities. To ensure uniform data collection, adherence to Sponsor procedures and

protocol understanding Sponsor will present a formal training session to study site personnel before study recruitment commences. During this training, navigation of EDC, source documents, protocol, mock retrospective entry, recruitment methods, and consenting documentation will be reviewed. The training will be documented and kept in study files.

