### PROTOCOL REVISION HISTORY

Protocol Revision	Revision Date	History
A	30 May 17	Initial Release
B	31 Jan 18	

1. Replaced unanticipated with unexpected adverse event throughout.

2. Clarified SAE reporting requirements

3. Replaced CEC with an Independent Safety reviewer.

4. Revised TWOC endpoint to 300 ml PVR.

5. Updated to note urodynamics testing may be performed at each study site if a testing facility is available and a qualified operator is on-site

6. Removed urodynamics and Active UTI from eligibility procedures

7. Clarified language surrounding procedure antibiotics

8. Clarified UA and urine culture requirements.

9. Removed Active Urinary Tract Infection and active gross hematuria from exclusion criteria

10. Removed reference to IPP size for inclusion for prospective arm

11. Revised exclusion criteria language for prospective arm: #5, #10 and #11

12. Revised inclusion criteria for retrospective arm: excl. #5 and #6

13. Revised exclusion criteria for retrospective arm: #3, #5 and added #8.

14. For retrospective arm, updated to include all site invasive BPH surgeries.

15. Removed reference to protocol deviation waivers & over-read for enrolment.

16. Removed refresher training

C	12 August 2018	

1. Removed symptom questionnaire requirements at screening.

Protocol Revision	Revision Date	History

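### Operator experience may be confounded with treatment in the PUL-versus-surgery comparison, because PUL operators are selected on experience while the surgical cohort has no operator criterion and no listed operator field

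*Combined protocol and SAP*

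**What the plan says.** **PUL arm.** Section 10.3.3 sets an operator threshold: "Selected Principal Investigators in the study will have performed a minimum of 30 UroLift procedures". Section 17.2 adds "Investigators responsible for treating subjects with the UroLift System have expert experience with the device", and section 13.8, under risk mitigation, says "Participating Investigators are highly experienced UroLift operators and experienced in clinical research". Section 13.9 counts experienced investigators, again with the 30-case minimum, among the factors that have kept clinical risk low.

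**Surgical arm.** Cases come from a list described in section 15.2: "Case abstractors will create a Master List of all invasive BPH surgeries (TURP, HoLEP, etc.) performed by the site from June 1, 2015" to 31 December 2015. The matching inclusion criterion in section 15.3.1 is "Underwent invasive BPH surgery (TURP, HoLEP, etc.) while in retention and performed by site between June 01, 2015 and December 31, 2015". Neither the inclusion list (15.3.1) nor the exclusion list (15.3.2) mentions the surgeon.

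**Data abstracted.** Section 15.8.2 lists date and duration, "Type of facility, type of surgery", complications and adverse events, length of stay, catheterisation and pathology. Sections 15.8.1 and 15.8.3 cover history and follow-up. None of the three lists names the operator, grade or case volume. On the prospective side, section 10.3.4 asks for the clinical staff needed during the procedure, but not for the operator or the operator's case count.

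**Analysis.** Section 16.6 (Retrospective Arm) compares procedure time and hospitalisation time by t-test or a non-parametric alternative, and binary items by chi-square or Fisher's exact test. It also says that statistical significance will be assessed for related AEs and SAEs, retreatment, retention recurrence, TWOC success and catheter use. It plans no adjustment or stratification.

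**The concern.** Section 6.1 makes it an objective to compare the benefits and risks of PUL with those of invasive surgery in a matched population, and section 13.9 expects that comparison to help show the benefit of PUL. The matching is on patient criteria only.

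Procedure time, stay, complications and retreatment can plausibly depend on who operates. By the protocol's own reasoning, operator experience lowers risk: sections 13.8 and 13.9 credit it with doing so for PUL. Such a factor, selected for in one arm and left both open and unlisted in the other, is a possible confounder of every outcome in the section 16.6 comparison.

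If the operator is not abstracted, the question cannot be examined at analysis. The study is also meant to inform a larger randomised trial (sections 7 and 13.9), so a distorted surgical benchmark could carry into its planning.

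**Working it through.** The plan gives no figure for the operator mix or for the retrospective sample size, so there is nothing to reproduce. The check is a comparison of the text, followed by an illustration.

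**Step 1. The arms side by side**

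| Item | PUL arm | Surgical arm |
|---|---|---|
| Operator criterion | At least 30 prior UroLift procedures (10.3.3, 13.9); described as expert (17.2) | None (15.2, 15.3.1, 15.3.2) |
| Source of cases | Prospective, by study investigators | All eligible invasive BPH surgery at the site, June to December 2015 |
| Operator among listed data items | No (10.3.4) | No (15.8.1 to 15.8.3) |
| Operator in the bias checklist (Table 12) | Not addressed | Not addressed; investigators' patient volume is cited only under whether enough charts exist |
| Adjustment or stratification in 16.6 | None stated | None stated |

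That surgery by any surgeon is eligible follows from the absence of a restriction; the protocol does not state it. Likewise, the operator is absent from the listed items, but the full eCRF is not in the documents.

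**Step 2. What an operator effect could do to a test in section 16.6**

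Inputs: 55 PUL subjects, the maximum in sections 1 and 7. Everything else is assumed: an event rate of p1 = 20% in one arm; no treatment effect; a rate of p2 = p1 + d in the other arm, with d due to operators alone; 30, 55 or 100 retrospective patients; two-sided alpha 0.05. PUL is given the lower rate only to fix the arithmetic. This is not a claim about direction.

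The chance of p < 0.05 in the direction of the shift, by the normal approximation, is

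Φ[(d − 1.96 × se0) / se1]

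with se0 = √[p̄(1 − p̄)(1/n1 + 1/n2)] and se1 = √[p1(1 − p1)/n1 + p2(1 − p2)/n2], where p̄ is the pooled rate.

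Worked case, 55 per arm and d = 0.10:
- p̄ = 0.25, so se0 = √(0.25 × 0.75 × 2/55) = 0.0826.
- se1 = √[(0.16 + 0.21)/55] = 0.0820.
- (0.10 − 1.96 × 0.0826)/0.0820 = −0.755, and Φ(−0.755) = 0.225.

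| Shift d from operators alone | 30 retrospective | 55 retrospective | 100 retrospective |
|---|---|---|---|
| 0 (nominal) | 2.5% | 2.5% | 2.5% |
| 5 points | 8% | 9% | 10% |
| 10 points | 19% | 23% | 26% |
| 15 points | 34% | 42% | 50% |
| 20 points | 51% | 63% | 73% |

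The chance of a misleading result rises with the size of the comparator. The bias in the estimated difference is d at every sample size.

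**The case against.** **The comparison is secondary and openly limited.** The primary assessment is the single-arm TWOC rate (6.2, 16.5). Section 16.6 says that the study is not powered for the comparison, section 15.7 acknowledges many sources of bias in retrospective series, and section 16.7 sets no success criterion. All of this stands and limits the weight of the point. It does not remove it: low power concerns precision, whereas confounding shifts the estimate, and section 16.6 still commits to significance testing.

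**Taking every operation is a safeguard.** Table 12 answers the risk of an unrepresentative sample by having all surgery in the window evaluated, and the Revision B entry, "For retrospective arm, updated to include all site invasive BPH surgeries", agrees with the current text. This also stands. Making a surgeon-selected subset the basis of the main comparison would bring back case selection and shrink a cohort already limited to seven months, up to six sites and consenting patients.

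**The eCRF may hold more than section 15.8 lists.** That is possible. The point is therefore about the listed items.

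**A stronger reading does not hold.** A reader might infer that the comparison favours PUL, as experts against all comers. The 30-case threshold is UroLift experience only, and nothing is said about the TURP or HoLEP experience of the 2015 surgeons, which could be lower or higher. Nor can the "20% rate of perioperative morbidity" given for TURP in section 4 be treated as an experienced-operator rate and scaled up to size the bias. It is quoted as a general rate and may already mix operators. The proctored first case in section 17.2 should not be counted as a skill standard either, since its stated purpose is data collection.

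**Conclusion.** The point holds as a possible confounder that the plan, as written, leaves unexaminable. PUL operators are selected on experience; the surgical cohort has no operator criterion; no operator item is listed for abstraction; and section 16.6 plans no adjustment. Operator experience may therefore be mixed with treatment in the comparisons of procedure time, stay, AEs and SAEs, retreatment and TWOC success.

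Neither direction nor size can be determined from the documents. The percentages in the working show only what an assumed shift would do to a test. The primary TWOC assessment in the PUL arm is not affected. This is a worthwhile and cheap improvement to a secondary comparison, and it does not threaten the study's main result.

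**What to change.** **Abstraction (15.8.2).** Add the operating surgeon's grade, whether the operation was done independently or under supervision, and a coded surgeon ID, each where the operation note gives it.

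**Prospective record (10.3.4).** Add the operator code and the operator's number of previous PUL cases.

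**Analysis (16.6).**
- Describe operators by arm.
- Keep the comparison with all eligible surgery as the main one.
- Add a sensitivity comparison restricted to surgery by fully qualified operators working independently, with the rule written down before abstraction starts.
- Say in the conclusions whether the result changes, and that some operator confounding remains in either case, because UroLift case counts and TURP or HoLEP experience share no common scale.

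**Cost.** A few extra fields per chart, some of which will be missing, and a smaller comparator in the sensitivity rows. The complete Master List and its protection against case selection are kept.
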